#### **10.3.2. Causality collection**

The Investigator will assess causal relationship between the IPs and each AE and answer “yes” or “no” to the question “Do you consider that there is a reasonable possibility that the event may have been caused by the investigational product?”

For SAEs causal relationship will also be assessed for other medication and study procedures. Note that for SAEs that could be associated with any study procedure, the causal relationship is implied as “yes.”

#### **10.3.3. A guide to the interpretation of the causality question is found in next section. Relationship to protocol procedures**

The Investigator is also required to provide an assessment of the relationship of SAEs to protocol procedures on the SAE report form. This includes both non-treatment-emergent (i.e., SAEs that occur prior to the administration of IP) and treatment-emergent SAEs. A

protocol-related SAE may occur as a result of a procedure or intervention required during the study (e.g., blood collection). The following guidelines should be used by Investigators to assess the relationship of SAEs to the protocol:

- Protocol related: The event occurred due to a procedure or intervention that was described in the protocol for which there is no alternative etiology present in the patient's medical record.
- Not protocol related: The event is related to an etiology other than the procedure or intervention that was described in the protocol. The alternative etiology must be documented in the study patient's medical record.

#### **10.3.4. Adverse events based on signs and symptoms**

All AEs spontaneously reported by the patient or reported in response to the open question from the study personnel: "Have you had any health problems since the previous visit/you were last asked?" or revealed by observation will be collected and recorded in the eCRF. When collecting AEs, the recording of diagnoses is preferred, when possible, to recording a list of signs and symptoms. However, if a diagnosis is known and there are other signs or symptoms that are not generally part of the diagnosis, the diagnosis and each sign or symptom will be recorded separately.

#### **10.3.5. Adverse events based on examinations and tests**

The results from protocol-mandated laboratory tests and vital signs measurements will be summarized in the CSR. Deterioration as compared to baseline in protocol-mandated laboratory values and vital signs should therefore only be reported as AEs if they fulfill any of the SAE criteria or are the reason for discontinuation of treatment with the IPs.

If deterioration in a laboratory value or vital sign is associated with clinical signs and symptoms, the sign or symptom will be reported as an AE and the associated laboratory result or vital sign will be considered as additional information. Whenever possible, the reporting Investigator should use the clinical rather than the laboratory term (e.g., anemia versus low hemoglobin value). In the absence of clinical signs or symptoms, clinically relevant deteriorations in nonmandated parameters should be reported as AEs.

Deterioration of a laboratory value that is unequivocally due to disease progression should not be reported as an AE/SAE.

Any new or aggravated clinically relevant abnormal medical finding at a physical examination as compared with the baseline assessment will be reported as an AE.

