**Table 6. Urinalysis**

Bilirubin	Ketones
Blood	pH
Color and appearance	Protein
Glucose	Specific gravity

Note: Microscopy should be used as appropriate to investigate white blood cells and use the high power field for red blood cells.

If a patient shows an AST or ALT  $\geq 3 \times$  ULN together with total bilirubin  $\geq 2 \times$  ULN, refer to Appendix 1 for further instructions on cases of increases in liver biochemistry and

evaluation of Hy's Law. These cases should be reported as SAEs if, after evaluation, they meet the criteria for a Hy's law case or if any of the individual liver test parameters fulfill any of the SAE criteria.

All patients should have further chemistry profiles performed at 30 days ( $\pm 3$  days), 2 months ( $\pm 1$  week) and 3 months ( $\pm 1$  week) after permanent discontinuation of IP (see Table 4).

Any clinically significant abnormal laboratory values should be repeated as clinically indicated and recorded on the eCRF. Situations in which laboratory safety results should be reported as AEs are described in Section 10.3.5.

All patients with Grade 3 or 4 laboratory values at the time of completion or discontinuation from IP must have further tests performed until the laboratory values have returned to Grade 1 or 2, unless these values are not likely to improve because of the underlying disease.

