## **10.1. Safety parameters**

### **10.1.1. Definition of adverse events**

An adverse event is the development of an undesirable medical condition (other than progression of the malignancy under evaluation) or the deterioration of a pre-existing medical condition following or during exposure to a pharmaceutical product, whether or not considered causally related to the product. An undesirable medical condition can be symptoms (e.g., nausea, chest pain), signs (e.g., tachycardia, enlarged liver) or the abnormal results of an investigation (e.g., laboratory findings, electrocardiogram). In clinical studies, an AE can include an undesirable medical condition occurring at any time, including run-in or washout periods, even if no study treatment has been administered.

The term AE is used to include both serious and non-serious AEs.

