### **10.1.3. Durvalumab + tremelimumab adverse events of special interest**

An adverse event of special interest (AESI) is one of scientific and medical interest specific to understanding of the Investigational Product and may require close monitoring and rapid communication by the investigator to the sponsor. An AESI may be serious or non-serious. The rapid reporting of AESIs allows ongoing surveillance of these events in order to characterize and understand them in association with the use of this investigational product.

AESIs for durvalumab ± tremelimumab include but are not limited to events with a

potential inflammatory or immune-mediated mechanism and which may require more frequent monitoring and/or interventions such as steroids, immunosuppressants and/or hormone replacement therapy. These AESIs are being closely monitored in clinical studies with durvalumab monotherapy and combination therapy. An immune-mediated adverse event (imAE) is defined as an AESI that is associated with drug exposure and is consistent with an immune-mediated mechanism of action and where there is no clear alternate etiology. Serologic, immunologic, and histologic (biopsy) data, as appropriate, should be used to support an imAE diagnosis. Appropriate efforts should be made to rule out neoplastic, infectious, metabolic, toxin, or other etiologic causes of the imAE.

If the Investigator has any questions in regards to an event being an imAE, the Investigator should promptly contact the Study Physician.

AESIs observed with durvalumab  $\pm$  tremelimumab include:

- Diarrhea / Colitis
- Intestinal perforation
- Pneumonitis / ILD
- ALT/AST increases / hepatitis / hepatotoxicity
- Neuropathy / neuromuscular toxicity (e.g. Guillain-Barré, and myasthenia gravis)
- Myositis/polymyositis
- Endocrinopathies (i.e. events of hypophysitis, hypopituitarism, adrenal insufficiency, diabetes insipidus, hyper- and hypothyroidism and type I diabetes mellitus)
- Rash / Dermatitis
- Nephritis / Blood creatinine increases
- Pancreatitis (or labs suggestive of pancreatitis - increased serum lipase , increased serum amylase).
- Myocarditis

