#### 11.2.2. Efficacy analyses and exploratory analyses

Table 8. *Efficacy analyses and exploratory analyses*

Objectives	Variable	Analysis	Clinical factors	Analysis population
Primary: efficacy of durvalumab plus tremelimumab with concurrent radiotherapy in terms of pathological response rate	Pathological response rate	1. Proportion estimation with a 95% confidence interval 2. Simon two stage decision rule 3. Logistic regression with clinical factors	Tumour size Tumour localization Histology Biomarkers	Per protocol
Secondary 1a: bladder preservation.	Rate of bladder preserved	1. Proportion estimation with a 95% confidence interval 2. Logistic regression with clinical factors	Tumour size Tumour localization Histology Biomarkers	Per protocol
Secondary 1b: bladder preservation.	Rate of immediate and late salvage cystectomies.	1. Proportion estimation with a 95% confidence interval 2. Logistic regression with clinical factors	Tumour size Tumour localization Histology Biomarkers	Per protocol

Secondary 1c: bladder preservation.	Time from start of immunotherapy to the date of recurrence of muscle invasive bladder carcinoma or metastases.	Kaplan Meier estimation of survival with a 95 % confidence interval	Not applicable	Per protocol
Secondary 1d: Overall survival	Time from treatment start to exitus.	Kaplan Meier estimation of survival with a 95 % confidence interval		Per protocol
Secondary 1.3: Progression free survival	Time from treatment start to tumour relapse or distant progression.	Kaplan Meier estimation of survival with a 95 % confidence interval		Per protocol
Secondary 2: Safety profile and tolerability of combination	CTCAE V4.03	1. Frequency table with adverse events, grades and relationship to study drugs and to radiotherapy treatment 2. Frequency table with severe toxicity.	Durvalumab cumulative dose, tremelimumab cumulative dose, radiotherapy treatment constraints (dose in risk organs).	Safety population
Secondary 3: To evaluate the long term functionalism and late sequel of the treatment in the preserved bladders.	Bladder control scale	Repeated measures analysis		Per protocol
Exploratory 1: Biomarkers and pathological response rate	Biomarkers and pathological response rate	Logistic regression in which response or not is the response and baseline biomarkers are factors to be studied	Biomarkers	Per protocol

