### 2.3.2. TOXICITIES GRADE $\geq 3$

Table 203: Toxicities with grade 3 or higher

Adverse Event (CTC)	N (%)
---------------------	-------

Table 204: List of all toxicities with grade 3 or higher

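### Protocol Section 10.3.5 keeps some non-serious laboratory toxicity off the adverse event form, contradicts Sections 10.1.1 and 10.1.3, and has no on-treatment laboratory table in the SAP to compensate

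*Combined protocol and SAP*

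**What the plan says.** Section 10.3.5 of the protocol restricts adverse event (AE) reporting for protocol-mandated laboratory values and vital signs: deteriorations "should therefore only be reported as AEs if they fulfill any of the SAE criteria or are the reason for discontinuation of treatment" with the investigational products. If symptoms accompany the change, the symptom is the AE and the laboratory result is supporting information. The reason given is that "The results from protocol-mandated laboratory tests and vital signs measurements will be summarized in the CSR".

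The notes after Table 6 make this the governing rule: "Situations in which laboratory safety results should be reported as AEs are described in Section 10.3.5". For tests outside the mandated panel the same section is more demanding: "In the absence of clinical signs or symptoms, clinically relevant deteriorations in nonmandated parameters should be reported as AEs".

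Two other sections pull the other way. Section 10.1.1 includes in the AE definition "the abnormal results of an investigation (e.g., laboratory findings, electrocardiogram". Section 10.1.3 lists events of special interest, which need not be serious. They include "ALT/AST increases / hepatitis / hepatotoxicity", blood creatinine increases, and raised lipase or amylase.

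On the analysis side, Table 8 of Section 11.2.2 bases the safety objective on a "Frequency table with adverse events, grades and relationship to study drugs and to radiotherapy treatment". The SAP's severe-toxicity output, such as "Toxicities with grade 3 or higher" (Table 203), is built on AE terms.

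**The concern.** Chemistry and haematology are mandated and tested repeatedly on treatment (Tables 4 and 5 and the schedule of assessments). The exception for non-mandated tests therefore does not help, and the most closely monitored laboratory toxicities get the weaker reporting rule. Appendix 1 manages several of them by withholding and then resuming study drug. If the patient has no symptoms, nothing serious follows and dosing resumes, Section 10.3.5 gives no reason to complete an AE form.

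Toxicity is part of the stated purpose of the study (Section 1) and safety is a secondary objective (Section 2.2). Omissions of this kind all lower the reported grade ≥3 rate. In addition, two sites among the seven could record the same event differently and each point to a section that supports it.

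**Working it through.** The plan states no figure on this point, so there is none to reproduce. The check is mainly of text, followed by two illustrations of size.

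**1. Which Grade 3-4 laboratory events can escape Section 10.3.5?** This sets Appendix 1 beside the two triggers (SAE criterion, or discontinuation of study drug).

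| Event | Appendix 1 action | Position under 10.3.5 |
|---|---|---|
| Non-immune Grade 3, e.g. blood counts | Hold; resume if improved within 7 or 14 days | Not an AE if non-serious, asymptomatic and resumed |
| Non-immune Grade 4 laboratory value | Discontinuation depends on signs, symptoms and judgement | Not an AE if non-serious, asymptomatic and drug not stopped |
| AST/ALT >5 to 8×ULN | Hold; resume if resolved within 14 days | Not an AE if non-serious, asymptomatic and resumed |
| Asymptomatic lipase/amylase >2×ULN | Hold; continue or resume if no pancreatitis | Not an AE if non-serious and resumed |
| AST/ALT >8×ULN | Permanent discontinuation | Recordable |
| Hy's law case | Permanent discontinuation; SAE under 8.2.5 and 10.3.9 | Recordable |
| Immune-mediated Grade 3-4 creatinine | Permanent discontinuation | Recordable |

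Appendix 1 gives the liver and pancreatic thresholds as multiples of ULN without a grade number. Treating them as Grade 3-4 is an assumption that depends on the actual value and CTCAE v4.03.

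One timing point adds to this. After the third dose (week 9 in the SAP treatment tables) no study drug remains to discontinue. A later asymptomatic abnormality inside the 12-week window can then qualify only through an SAE criterion.

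**2. Which events have a competing route?** Liver, creatinine and lipase/amylase rises are named in Section 10.1.3. Low blood counts are not named. Haematological events appear there only as a general category among rare, possibly immune-mediated reactions. The gap is therefore clearest for blood counts.

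**3. Would another table show the event?** SAP Sections 3.2.5 to 3.2.7 tabulate laboratory values at baseline only. Tables 29, 30 and 33 to 35 (missed or delayed doses) and 37 to 38 (radiotherapy interruptions) can give a reason, but no CTCAE grade. Tables 198, 203, 204, 207 and 208 use AE records.

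**4. Size in the safety tables (assumed rate).** Suppose 5-15% of patients have such an event and none is recorded: 32 × 0.05 = 1.6 and 32 × 0.15 = 4.8, so about 2 to 5 patients. As a share, 2/32 = 6.3% and 5/32 = 15.6%.

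**5. Size in the run-in, if its count came from AE forms (assumed rates).** The rule is ≥2 of 5 patients, then ≥1 of 3. With true rate p and recorded share c, the counted rate is q = p × c and

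P(modify) = P(X ≥ 2 | 5, q) × P(Y ≥ 1 | 3, q).

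- p = 0.40, c = 1: (1 − 0.6⁵ − 5 × 0.4 × 0.6⁴) × (1 − 0.6³) = 0.663 × 0.784 = 0.520.
- p = 0.40, c = 0.75, so q = 0.30: 0.472 × 0.657 = 0.310.

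| True rate p | All recorded | 75% recorded | 50% recorded |
|---|---|---|---|
| 0.2 | 0.128 | 0.064 | 0.022 |
| 0.3 | 0.310 | 0.168 | 0.064 |
| 0.4 | 0.520 | 0.310 | 0.128 |
| 0.5 | 0.711 | 0.468 | 0.212 |

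**The case against.** The strongest reply is that this is a conflict of wording and not a demonstrated loss of data. Sections 10.1.1 and 10.1.3 give investigators grounds to report liver, renal and pancreatic rises. Sections 6.1.2 and 10.1.3 describe Appendix 1 as applying to AEs judged causally related, so an investigator who holds a dose under it is arguably already treating the finding as an AE. Section 10.3.4 prefers diagnoses, so a treated ALT rise may be entered as hepatitis. The important-medical-event criterion in Section 10.1.2 may cover some cases needing intervention. Finally, Section 10.3.5 promises the laboratory summary in the clinical study report, whereas the SAP carries a manuscript title. Its lack of an on-treatment table does not prove that the report will lack one.

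Much of this stands. A reader might infer that Section 10.3.5 removes liver, pancreatic, renal and haematological toxicity from the safety tables as a matter of course. The documents do not support that: there is a competing route for most of these, and the most severe liver and immune-mediated renal events lead to discontinuation and so are recordable during dosing.

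A reader might also infer that the run-in misses these events. That is not shown either. The run-in text (synopsis safety assessments, Sections 3.1 and 11.2.3) defines neither dose-limiting toxicity nor where the count comes from, and safety bloods must be reviewed before each infusion.

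What the reply does not remove is that Section 8.2.5 names 10.3.5 as the governing text, that blood counts have no named alternative, and that neither the protocol nor the SAP specifies an on-treatment laboratory grade table.

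**Conclusion.** The point holds as an internal contradiction with a one-directional risk. Where sites follow Section 10.3.5, asymptomatic, non-serious Grade 3-4 laboratory toxicity managed by hold and resumption can be missing from the grade ≥3 tables, with no planned SAP table to reveal it. This is clearest for blood counts. It also applies to AST/ALT >5 to 8×ULN and to lipase/amylase, subject to the grade assumption stated in the working.

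The 2 to 5 patients in 32 is an illustration at the assumed rates. It is a ceiling for those rates because it supposes that every such event goes unrecorded. The run-in probabilities are conditional on assumed rates and on a count taken from AE forms, which the documents do not state. They show why the source matters, not that the run-in is biased. The primary endpoint and the Simon decision rule are unaffected. I regard this as a moderate point that is worth correcting because correction is cheap.

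**What to change.** 1. Reconcile Section 10.3.5 with 10.1.1 and 10.1.3, so that a mandated laboratory deterioration is recorded as an AE when it is CTCAE Grade ≥3, leads to a hold or delay of study treatment, or is a listed event of special interest. This changes recording only, not management.
2. Add to the SAP a table of worst on-treatment CTCAE grade against baseline for each mandated analyte that has a CTCAE grade. Section 8.2.5 already requires results, units and reference ranges in the eCRF. The SAP already describes 32 patients as meeting the population conditions, so this table is the part that can still help with data in hand.
3. Ask the sponsor to reconcile the run-in passages, which use dose-limiting and severe toxicity interchangeably, by stating the definition and the data source for the count. The choice of definition is a clinical matter for the sponsor.

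The cost is a short protocol amendment, one extra table and some additional AE entries. The reported grade ≥3 rate may look less favourable.

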#### **10.3.6. Hy's Law**

Cases where a patient shows elevations in liver biochemistry may require further

evaluation and occurrences of AST or ALT  $\geq 3 \times$  ULN together with total bilirubin  $\geq 2 \times$  ULN may need to be reported as SAEs. Please refer to Appendix 1 for further instruction on cases of increases in liver biochemistry and evaluation of Hy's law.

#### **10.3.7. Disease progression**

Disease progression can be considered as a worsening of a patient's condition attributable to the disease for which the IP is being studied. It may be an increase in the severity of the disease under study and/or increases in the symptoms of the disease. The development of new or progression of existing metastasis to the primary cancer under study should be considered as disease progression and not an AE. Events that are unequivocally due to disease progression should not be reported as an AE during the study.

#### **10.3.8. New cancers**

The development of a new cancer should be regarded as an SAE. New primary cancers are those that are not the primary reason for the administration of the IP and have been identified after the patient's inclusion in this study.

#### **10.3.9. Reporting of serious adverse events**

All SAEs will be reported, whether or not considered causally related to the investigational product, or to the study procedure(s). The reporting period for SAEs is the period immediately following the time that written informed consent is obtained through 90 days after the last dose of durvalumab or until the initiation of alternative anticancer therapy. The investigator and/or Sponsor are responsible for informing the Regulatory Authority of the SAE as per local requirements.

Each AE is to be assessed to determine if it meets the criteria for SAEs. If an SAE occurs, expedited reporting will follow local and international regulations, as appropriate.

The sponsor must inform the AEMPS of any Suspected serious or unexpected serious adverse events (SUSAR) that occur in accordance with the reporting obligations, and will concurrently forward all such reports to AstraZeneca. A copy of the report must be sent by e-mail to AstraZeneca at the time the event is reported to the AEMPS by the sponsor.

\* A cover page should accompany the SAE form indicating the following:

- External Scientific Research (ESR)
- The investigator's name and address
- The trial name/title and AstraZeneca ESR reference number

\* Send SAE report and accompanying cover page by way of Email to

If a non-serious AE becomes serious, the same process described before will be followed.

Serious adverse events that do not require expedited reporting to the AEMPS need to be reported to AstraZeneca preferably using the MedDRA coding language for serious adverse events. This information should be reported on a monthly basis and under no circumstance less frequently than quarterly.

The following reportable events must be submitted to the sponsor within 24 hours (or immediately for death or life-threatening events).

### *Serious Adverse Events*

- Exposure during Pregnancy or Breastfeeding (even if not associated with an adverse event).
- Occupational exposure (even if not associated with an adverse event)
- Potential drug-induced liver injury (Hy's Law cases): These events are considered important medical events and should be reported as SAEs.

Site staff should send SAE report and accompanying cover page by fax or email to sponsor/CRO's designated mailbox:

#### *10.3.9.1. Reporting of deaths to*

All deaths that occur during the study, or within the protocol defined 90 day post last dose of durvalumab + tremelimumab safety follow up period must be reported to the sponsor as follows:

- Death that is clearly the result of disease progression should be documented but should not be reported as an SAE.
- Where death is not due (or not clearly due) to progression of the disease under study, the AE causing the death must be reported to the sponsor as a SAE within **24 hours** (see Section 10.3.2 for further details). The report should contain a comment regarding the co-involvement of progression of disease, if appropriate, and should assign main and contributory causes of death.
- Deaths with an unknown cause should always be reported as a SAE.

*Deaths occurring after the protocol defined safety follow up period after the administration of the last dose of study drug should be documented in the Statement of Death page. If the death occurred as a result of an event that started after the defined*

*safety follow up period and the event is considered to be due to a late onset toxicity to study drug, then it should also be reported as an SAE.*

